#### 10.7.2.1.1 *Definition of intercurrent events (IEs)*

1. IEs related to COVID-19 pandemic are confirmed if:

- AE term AEDECOD is 'SARS-CoV-2 test positive' in the sdtm database. The AE start date AESTDTC will be considered to assign missing values (as defined in bullet 1 of Section 10.7.2.2) to all assessments following this date and up to and including Week 6 D40.

2. Intake of prohibited medications/therapies defined in APPENDIX C will be finalized and flagged accordingly on a case-by-case basis by a Sponsor medical review of the concomitant medications as defined in Section 8.4.3. The CM start date will be considered to assign missing values (as defined in bullet 2 of Section 10.7.2.2) to all assessments following this date and up to and including Week 6 D40.
3. Other IEs leading to treatment/study discontinuation (except those related to COVID- 19 pandemic) are confirmed if:

the action taken AEACNOTH of the corresponding adverse event is 'DRUG DISCONTINUED' or 'SUBJECT WITHDRAWAL' in the sdtm database and subject had study assessments after the AE onset date AESTDTC and up to and including Week 6 D40.

In all cases if the date of the assessment and the IE start date occur in the same date, this assessment values will be assigned to missing.

If the date of assessments following the IE start date are missing, these will be imputed based on the theoretical date the assessments should have been occurred:

- if the IE start date <= study day 9 then both Week 2 and 6 assessments have to be set to missing and imputed
- if the IE start date is between study day 10 and 44 then Week 6 assessment has to be set to missing and imputed

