13.6.4. Sample size determination

Randomizing 26 subjects per arm, if the true efficacy of MM-120 reaches a standardized mean improvement over placebo of 0.60, the null hypothesis that active is not better than placebo will be rejected with a one-sided p-value < 0.10 with 80% power.

The minimum estimated standardized effect size resulting in a p-value < 0.10 is 0.38 while an estimated standardized effect size < 0.56 will result in a one-sided p-value < 0.025.

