## 2 TRIAL DESIGN, STUDY DOCUMENTS, DATABASE CODING

### 2.1 TRIAL DESIGN

#### 2.1.1 Trial design

This is a randomized, double-blind, placebo-controlled, Phase 2a study on the efficacy and safety of repeated low dose D-lysergic acid diethylamide (LSD) D-Tartrate (MM-120) in adult subjects aged  $\geq 18$  and  $\leq 65$  with attention-deficit/hyperactivity disorder (ADHD).

Eligible subjects that consent to participate will be randomized in a 1:1 allocation to placebo or MM-120.

There will be 2 arms:

- Arm 1-Placebo: a total of 26 subjects will receive a placebo identical in appearance to the IMP administered orally twice weekly for 6 weeks. Subjects and site staff will remain blinded to the treatment group.
- Arm 2-MM-120: a total of 26 subjects will receive 20  $\mu$ g of MM-120 twice weekly for 6 weeks. Subjects and site staff will remain blinded to the treatment group.

Potential study subjects who provide informed consent will have eligibility evaluated/confirmed at 2 visits: 1) Screening, and 2) Baseline. The screening visit occurs up to 4 weeks prior to Baseline. An assessment will be made to confirm or make the ADHD diagnosis with the Mini International Neuropsychiatric Interview (MINI). The subject must have an Adult Attention Deficit Investigator Symptom Rating Scale (AISRS) score of  $\geq 26$  and a Clinical Global Impression - Severity of Illness Scale (CGI-S) score of  $\geq 4$  at screening and must meet all other eligibility criteria:

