## 8.7 TRIAL DISCONTINUATION

Subjects with premature trial termination are identified as those with answer 'No' to the question 'Did the subject complete the study?' in the “Termination Form” CRF section.

The reasons that can be associated with the trial discontinuation are:

- Lost to follow-up;
- Death;
- COVID-19 related;
- Other (to be specified).

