### 10.7.1 Statistical model and hypotheses

The null hypothesis is that active MM-120 is not better than placebo; this will be rejected with a one-sided p-value < 0.10 with 80% power if the true efficacy of MM-120 reaches a standardized mean improvement over placebo of 0.60.

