#### **10.7.2.2 Analysis details**

Primary endpoint, change in AISRS score from baseline to Week 6, will be analyzed applying Rubin's rule to a multiple imputations procedure to appropriate contrasts based on Mixed Model for Repeated Measures (MMRM) analysis of covariance with the change in the AISRS score from baseline to Week 2 and Week 6 visits as dependent variable, and treatment group, visit, visit-by-treatment group interaction, baseline score of AISRS, sex and age as fixed effects. An unstructured variance-covariance matrix will be used to model within-subject errors. Satterthwaite's method will be used to approximate the degrees of freedom. If convergence problems arise (even just in one imputed dataset) the following order of matrices will be applied: Heterogeneous TOEP (TOEPH), Toeplitz (TOEP), Autoregressive(1) (AR(1)). The same variance-covariance matrix will be used in sensitivity analyses.

The imputation model include the longitudinal sequence of AISRS Scores, and the covariates used in the model as defined above. As a general approach, imputations are performed on observed values specifying a minimum and a maximum threshold (zero and 54 respectively) for AISRS. The change from baseline in AISRS Scores will not be imputed to avoid imputation of nonsensical values. For the imputation of missing data of AISRS, one thousand (1000) data sets will be generated, and the random seed number will be 200208. MI will be implemented following the steps below:

1. Imputation assuming a MAR (policy strategy 1).

MAR will be applied following the steps below:

- a)all assessments that took place after the IEs related to COVID-19 pandemic will be kept in the database;
- b)imputing all missing values already present in the data.

MI will be carried out based on fully conditional specification method (FCS, the details will be provided in the 'Programming standards and conventions' document). These datasets will be utilized in Step #2.

2. Imputation assuming MNAR (policy strategy 2).

MNAR will be applied following the steps below:

- a)assigning missing values to all assessments that took place after the IEs specified in policy strategy 2 above;
- b)imputing missing values assigned at step (a).

MNAR assumption based on copy reference approach (i.e. using the non-missing values of the placebo arm) will be used.

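### SAP 10.7.2.1.1 tells the programmer to blank AISRS scores after a COVID-19 event that the estimand keeps, and its single-term definition could send some COVID-19 discontinuations to placebo-based imputation

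*SAP*

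**What the plan says.** SAP 10.7.2.1 sets two strategies for intercurrent events. Strategy 1 covers COVID-19 events and other intercurrent missing data: observed scores are used and gaps are imputed under MAR from the same arm. Strategy 2 covers prohibited medication and other events leading to discontinuation, with COVID-19 excepted: scores after the event are removed and imputed from placebo.

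SAP 10.7.2.1.1 then defines the events.

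- **Item 1.** A COVID-19 event is confirmed if "AE term AEDECOD is 'SARS-CoV-2 test positive' in the sdtm database". The item continues: "The AE start date AESTDTC will be considered to assign missing values (as defined in bullet 1 of Section 10.7.2.2"), applied to all assessments after that date up to and including Week 6 D40.
- **Item 3.** Other discontinuation events are confirmed when an AE carries the action drug discontinued or subject withdrawal and the subject has later assessments. COVID-19-related events are again excepted.
- **Closing rules.** A score dated on the event start date is set to missing, whatever the type of event. Where the assessment date is missing, scores are set to missing according to whether the event began by study day 9 or on days 10 to 44.

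SAP 10.7.2.2 step 1a says "all assessments that took place after the IEs related to COVID-19 pandemic will be kept in the database". Step 1b imputes only values that are already missing. Separately, SAP 8.7 lists "COVID-19 related" among the Termination Form reasons. The event definition does not use it.

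**The concern.** Item 1 reads as an instruction to delete. Item 2 uses the same construction for prohibited medication, and there deletion is meant (10.7.2.2 step 2a). A programmer working from the definitions section could reasonably blank valid Week 2 and Week 6 AISRS scores, while one working from 10.7.2.2 would keep them. The primary data set should follow from the SAP without that choice.

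The consequences go beyond the main model. The key secondary analysis (10.8.1.1) uses the same estimand and imputation process. The tipping-point and copy-reference sensitivity analyses (10.7.3.1, 10.7.3.2) act on missing data from both strategies. If post-COVID scores had been blanked, observed MM-120 scores would be replaced there by delta-worsened or placebo-based values, which moves the estimate as well as its precision.

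The definition raises a second problem. Item 3 excepts COVID-19 events, but item 1 is the only place that says what they are. A COVID-19 illness coded to a different term could miss the exception.

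**Working it through.** **1. The texts side by side, for AISRS scores observed after a COVID-19 event**

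| Place | Treatment of the score |
|---|---|
| Protocol 13.6.1 | Use |
| SAP 10.7.2.1, strategy 1 | Use |
| SAP 10.7.2.2, steps 1a and 1b | Keep; impute only existing gaps |
| SAP Appendix B, version 2.0, item 12 | Keep |
| SAP 10.7.2.1.1, item 1 | Assign missing through Week 6 D40 |
| SAP 10.7.2.1.1, same-day rule | Set to missing, all event types |
| SAP 10.7.2.1.1, missing-date rule | Set to missing, not limited to strategy 2 |

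The cross-reference in item 1 leads to a bullet that assigns no missing values. Appendix B lists the event definitions (item 11) and the keep rule (item 12) as version 2.0 changes, and the two were not reconciled.

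**2. Routing under the single-term rule**

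- COVID-19 illness coded to another term, action drug discontinued or subject withdrawal, later assessments present: not confirmed under item 1 and meets the conditions of item 3. Whether the exception rescues it depends on whether *COVID-19-related* means only what item 1 confirms.
- Termination reason "COVID-19 related" with no such AE: item 3 is not met, and step 1b imputes the gap under same-arm MAR. This is the intended strategy.

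**3. The plan's own power figure**

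Inputs: "Randomizing 26 subjects per arm" (Protocol 13.6.4); allocation "randomized in a 1:1 allocation to placebo or MM-120" (SAP 2.1.1); the null hypothesis, of which SAP 10.7.1 says "this will be rejected with a one-sided p-value < 0.10 with 80% power" if efficacy "reaches a standardized mean improvement over placebo of 0.60".

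Power = P(T > t(0.90; 2n − 2)), with T noncentral t and noncentrality 0.60·√(n/2). For n = 26: df = 50, critical value 1.299, noncentrality 2.163, power 80.6%. The stated 80% is reproduced.

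**4. Effect of discarding scores**

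Assumption: 5% to 15% of 52 subjects have a qualifying event before a recorded score. That is 2.6 to 7.8, about 3 to 8 subjects, or 1.5 to 4 per arm. Treating those scores as wholly lost:

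| n per arm | Power |
|---|---|
| 26 | 80.6% |
| 24.5 | 78.8% |
| 24 | 78.2% |
| 22 | 75.5% |

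This is the worst case, because MAR imputation recovers part of the information. If k scores per arm are discarded and ρ is the Week 2 to Week 6 correlation (assumed), the variance of the difference in SD units is

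V = 2/26 + (2/(26 − k) − 2/26)(1 − ρ²), and power ≈ Φ(0.60/√V − 1.282).

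- k = 0: V = 0.0769, power 81.1% (normal approximation).
- k = 1.5, ρ = 0.5: V = 0.0805, power 79.8%.
- k = 4, ρ = 0.5: V = 0.0769 + 0.0140 × 0.75 = 0.0874, power 77.3%.

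The two readings can also reach different decisions in the same trial. Simulating the keep estimate with variance 2/26 and adding independent noise of variance V − 2/26, at a true effect of 0.60, the one-sided 0.10 decision differs in about 4%, 8% and 12% of trials for k = 1, 3 and 5 with ρ = 0, and in about 4%, 7% and 10% with ρ = 0.5.

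**5. Effect of misrouting to placebo-based imputation**

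If the whole effect is lost in m of 26 MM-120 subjects, the expected difference is 0.60 × (1 − m/26): 0.577 for m = 1 and 0.554 for m = 2. An observed Week 2 score would soften this.

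**The case against.** The strongest reply is that item 1 does not stand alone. It assigns missing values only as bullet 1 of 10.7.2.2 defines them, and that bullet keeps the data. A reader might infer that the SAP contains two instructions of equal weight and that the intended data set cannot be known. The documents do not support that: both estimands, step 1a and the change list all point to keeping. What remains is that the words in item 1 and the two closing rules still direct deletion, and following the cross-reference only shows that those words are wrong.

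A reader might also infer that every COVID-19 illness coded differently goes to placebo-based imputation. That is too strong. Item 3 and strategy 2 both except COVID-19 events, so misrouting needs a different coded term, a discontinuation action, later assessments and a narrow reading of the exception. It is possible because item 1 supplies the only definition, but it is not certain.

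Nor does ignoring the Termination Form reason do much harm by itself, as the routing check shows.

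Finally, the complete-case analysis (10.7.3.3) ignores both strategies and keeps every observed score, so it would help reveal the effect of blanking. It is a sensitivity analysis and does not settle which data set is primary.

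**Conclusion.** The concern holds in a limited form. Item 1 of SAP 10.7.2.1.1 is wrong as written, and the same-day and missing-date rules reach COVID-19 events that the estimand treats differently. The evident intent is to keep the data. The single-term definition leaves a conditional route by which a COVID-19 discontinuation could be imputed from placebo, against the stated exception.

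The size is unknown because the documents give no COVID-19 count. On the assumed 1.5 to 4 discarded scores per arm, power at 0.60 falls from 80.6% to at worst about 79% to 75%. It should not be read as an expected loss: with an assumed correlation of 0.5 and Week 2 observed, the normal approximation goes from 81.1% to 79.8% to 77.3%. In the main analysis both readings impute under same-arm MAR, so the cost is mainly precision, with bias only if MAR fails. If no subject has a qualifying event on or before a recorded post-baseline AISRS, the readings give the same data set.

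**What to change.** In SAP 10.7.2.1.1:

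1. Delete the sentence in item 1 that assigns missing values, and say that observed scores after a COVID-19 event are used.
2. Limit the same-day rule and the missing-date rule (day 9; days 10 to 44) to strategy-2 events.
3. Define COVID-19 events by a list of COVID-19 infection terms reviewed blind to treatment, supplemented by the "COVID-19 related" termination reason. A rule that accepts any term naming the virus would be too wide, since it would take in negative tests and vaccine reactions.
4. State in item 3 that events meeting this definition are excluded from it.

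The cost is SAP wording, a short blinded term review and a matching change to the derivation program. No new data are needed. The changes belong before unblinding, the point by which Protocol 13.1 requires the SAP to be final. If the derivation has already been programmed, the report should say which reading it follows and how many scores were affected.

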13.6 Efficacy Analyses

13.6.1. Primary estimand

The primary estimand quantifies the treatment effect of MM-120 at 6-weeks vs placebo after twice weekly administration while accounting for intercurrent events (IEs) with potential confounding effects and IEs leading to study discontinuation prior to the 6-week assessment.

The following attributes describe the primary estimand:

- Population: As defined by the Inclusion/Exclusion criteria
- Endpoint: Change from baseline to Week 6 in the AISRS Score
- Treatment of interest: the randomized treatment MM-120 or placebo as a twice weekly treatment.
- Handling of intercurrent events (IEs) prior to AISRS assessments.
 - Intake or change in concomitant medications/therapies which have potential confounding effects
 - Intake of prohibited medications/therapies
 - Other IEs leading to treatment/study discontinuation (except those related to COVID-19 pandemic).

- Policy strategy. Available data recorded after the IE will be set to missing; such missing data will be imputed/substituted under a MNAR assumption by borrowing information from the placebo arm subjects (reference-based imputation).
- IEs related to COVID-19 pandemic and other intercurrent missing data
- Policy strategy. Available data will be used; missing data will be imputed under a MAR assumption by borrowing information from subjects in the same treatment arm.
- Summary measure: Difference between MM-120 and placebo in mean change from baseline to Week 6 for AISRS Score.

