13.6.3. Handling of missing/potentially biased values

Missing/potentially biased data will be imputed using a multiple imputation approach assuming that the missingness mechanism can be retrieved from observed data. The imputation model will include the longitudinal sequence of AISRS Scores, and the covariates used in the model as appropriate.

Depending on the IE causing the missing or potentially biased value, for:

- Intake or change in concomitant medications/therapies which have potential confounding effects
- Intake of prohibited medications/therapies
- Other IEs leading to treatment/study discontinuation (except those related to COVID-19 pandemic).

The data recorded after the IE will be imputed/substituted under a MNAR assumption by borrowing information from the placebo arm subjects (reference-based imputation).

For:

- IEs related to COVID-19 pandemic and other intercurrent missing data

Missing data will be imputed under a MAR assumption, borrowing information from subjects in the same treatment arm.

The full detailed information about the multiple imputation algorithms will be specified in the SAP.

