**Table 2: Scheduled Visit Window and Mapping of Assessments**

Assessment	Scheduled Visit Number	Scheduled Time point	Label on output	Target Study Day*	Time Interval Lower Limit (Day*)	Time Interval Upper Limit (Day*)
laboratory	Baseline	Baseline - Week 1D1	Baseline	1	No Lower limit	1
	Week 2	Week 1D5- Week 3D19	Week 2	15	2	21
	Week 4	Week 4 D22- Week 5 D33	Week 4	29	22	35
	Week 6	Week 6 D36 - Week 6 D40	Week 6	43	36	EOT
	Week 10 Follow-up/ Final visit for withdrawals	Week 10 Follow-up/ Final visit for withdrawals	Week 10 Follow-up/ Final visit for withdrawals	70	EOT+1	No Upper limit
Physical examination, ECG	Baseline	Baseline - Week 1D1	Baseline	1	No Lower limit	1
	Week 6	Week 6 D36 - Week 6 D40	Week 6	43	2	EOT
	Week 10 Follow-up/ Final visit for withdrawals	Week 10 Follow-up/ Final visit for withdrawals	Week 10 Follow-up/ Final visit for withdrawals	70	EOT+1	No Upper limit
Pregnancy test	Baseline	Baseline - Week 1D1	Baseline	1	-24	1
	Week 2	Week 1D5- Week 3D19	Week 2	15	2	21
	Week 4	Week 4 D22- Week 5 D33	Week 4	29	22	EOT
	Week 10 Follow-up/ Final visit for withdrawals	Week 10 Follow-up/ Final visit for withdrawals	Week 10 Follow-up/ Final visit for withdrawals	70	EOT+1	No Upper limit
Questionaries						
ASRS, CAARS-L-SR	Baseline	Baseline - Week 1D1	Baseline	-1	No Lower limit	-1
	Week 2	Week 1D5- Week 3D19	Week 2	15	2	21
	Week 4	Week 4 D22- Week 5 D33	Week 4	29	22	34

	Week 6	Week 6 D36	Week 6 D36	36	35	38
	Week 6	Week 6 D40	Week 6 D40	40	39	EOT
	Week 10 Follow-up/ Final visit for withdrawals	Week 10 Follow-up/Final visit for withdrawals	Week 10 Follow-up/ Final visit for withdrawals	70	EOT+1	No upper limit
AISRS, CGI	Baseline	Baseline	Baseline	1	No Lower limit	1
	Week 2	Week 2 D8	Week 2	8	2	21
	Week 6	Week 6 D40	Week 6	40	35	EOT
	Week 10 Follow-up/ Final visit for withdrawals	Week 10 Follow-up/Final visit for withdrawals	Week 10 Follow-up/ Final visit for withdrawals	70	EOT+1	No upper limit
Pharmacodynamics: SD-ASC**, MEQ- 30**, VAS***	Week 1 D1	Week 1 D1	Week 1 D1	1	NA	5
	Week 6	Week 6 D40	Week 6	40	NA	No upper limit

\* Relative to Study Day 1

\*\*No baseline assessment, post-dose at Week 1 D1

#No assessment at Week 6, only at visit Week1 D1 post-dose

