### 10.7.2 Main analysis

#### 10.7.2.1 Estimand

The primary estimand quantifies the treatment effect of MM-120 at 6-weeks vs placebo after twice weekly administration while accounting for intercurrent events (IEs) with potential confounding effects and IEs leading to study discontinuation prior to the 6-week assessment.

The following attributes describe the primary estimand:

- Population: Subjects in the FAS
- Endpoint: Change from baseline to Week 6 in the AISRS Score
- Treatment of interest: the randomized treatment MM-120 or placebo as a twice weekly treatment.
- Handling of intercurrent events (IEs) prior to AISRS assessments.

Depending on the IE causing the missing or potentially biased value, two sequential policy strategies will be applied:

1. Policy strategy. Available data will be used; missing data will be imputed under a Missing At Random (MAR) assumption by borrowing information from subjects in the same treatment group in following cases:
  - IEs related to COVID-19 pandemic and other intercurrent missing data (see details in Section 10.7.2.1.1).
2. Policy strategy. Available data recorded after the IE will be set to missing; such missing data will be imputed/substituted under a Missing Not At Random (MNAR) assumption by borrowing information from the placebo arm subjects (reference-based imputation) in following cases:
  - Intake of prohibited medications/therapies with potential confounding effect (APPENDIX C) (see details in Section 10.7.2.1.1).
  - Other IEs leading to treatment/study discontinuation (except those related to COVID-19 pandemic (see details in Section 10.7.2.1.1)).

- Summary measure: Difference between MM-120 and placebo in mean change from baseline to Week 6 for AISRS Score.

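### Non-COVID discontinuations without a coded adverse event are imputed from the subject's own arm, although the primary estimand, on its better reading, sends them to placebo-based imputation

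*SAP*

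**What the plan says.** **Scope of the estimand.** SAP 10.7.2.1 says that the estimand accounts for "IEs leading to study discontinuation prior to the 6-week assessment". Protocol 13.6.1 names as a class "Other IEs leading to treatment/study discontinuation (except those related to COVID-19 pandemic"), and SAP 10.7.2.1 repeats it under strategy 2. For this class protocol 13.6.3 states: "The data recorded after the IE will be imputed/substituted under a MNAR assumption by borrowing information from the placebo arm subjects".

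**The MAR class.** Strategy 1 imputes from the same treatment group for "IEs related to COVID-19 pandemic and other intercurrent missing data". SAP 10.7.2.1 refers to 10.7.2.1.1 for details. That section defines COVID-19 events, prohibited medication and coded discontinuation, but not the residual missing-data category.

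**The operational rule.** Item 3 of SAP 10.7.2.1.1 requires an adverse event with one of two action codes "in the sdtm database and subject had study assessments after the AE onset date AESTDTC and up to and including Week 6 D40".

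**The imputation order.** In SAP 10.7.2.2, step 1 works under MAR by "imputing all missing values already present in the data". Step 2 begins by "assigning missing values to all assessments that took place after the IEs specified in policy strategy 2 above" and then imputes those values from placebo.

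**The visit window.** Table 2 opens the AISRS Week 6 window at Day 35 and closes it at EOT, which SAP 11.1.1.3 defines as the last day of drug intake. Any later score is labelled "Week 10 Follow-up/ Final visit for withdrawals".

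**The concern.** Protocol 3.1 and 5.6 foresee discontinuation by the subject's own decision, for pregnancy and for noncompliance. SAP 8.7 records premature termination on a Termination Form whose reasons include loss to follow-up and an open category. Item 3 does not use that form. A leaver with no coded adverse event and no flagged medication thus has no event date, and step 2 cannot reach that subject.

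If the drug works, own-arm MAR credits active-arm leavers with the benefit seen in subjects who stayed. The primary Week 6 difference would then exceed the one the estimand defines. Placebo-arm leavers are imputed from placebo either way, so the shift runs in one direction. The primary result also decides whether the Week 2 AISRS comparison counts as confirmatory. SAP Appendix D, which lists changes from the protocol, does not mention this narrowing.

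**Working it through.** **1. One subject followed through the rules (illustration).** An MM-120 subject takes the last dose on Day 19 by own choice, with no coded adverse event and no flagged medication.
- Items 1 to 3 of SAP 10.7.2.1.1 all fail. The same-day rule and the theoretical-date rule both start from an event date, so neither applies.
- Week 6 is missing whether or not the subject is seen again. EOT is Day 19, so an AISRS on Day 40 maps to the final visit. A Day 40 AISRS after a last dose on Day 36 is lost in the same way.
- Step 1b fills Week 6 from the MM-120 arm. Step 2a has no event to act on.

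**2. Coded leavers with no later assessment.** The later-assessments condition excludes them. Yet the theoretical-date rule (event by Day 9: Weeks 2 and 6; Day 10 to 44: Week 6) provides for subjects whose later assessments are missing. The two parts of the section conflict.

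**3. The plan's own figure.** With 26 per arm, effect 0.60 SD and one-sided 0.10 (protocol 13.6.4), the noncentrality is 0.60/√(2/26) = 2.163 on 50 df. Power is 0.806 (0.811 by the normal approximation), so the stated 80% reproduces. I take 0.60 as the on-treatment effect.

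**4. Shift per misrouted active leaver.** Neither document gives a dropout rate or a correlation. Assumed:
- Week 2 to Week 6 correlation ρ of 0.4 to 0.6, with equal variances at the two visits
- Week 2 effect d2 of 0.3 to 0.6 SD
- a share f of 0 to 0.5 of leavers gone before Week 2
- equal numbers of leavers in the two arms

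Own-arm MAR gives a leaver an expected effect of 0.60. Placebo-based imputation gives ρ·d2 if a Week 2 score exists and 0 if not. The excess in the arm difference is:
- with a Week 2 score, (0.60 − ρ·d2)/26: from (0.60 − 0.36)/26 = 0.009 to (0.60 − 0.12)/26 = 0.018
- without one: 0.60/26 = 0.023

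That is 1.5% to 3.8% of 0.60 per subject.

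**5. Totals.** With L active leavers, of whom k are misrouted, the expected estimate is 0.60 − (L − k)/26 × [f × 0.60 + (1 − f)(0.60 − ρ·d2)]. The bracket runs from 0.24 (f = 0, ρ = 0.6, d2 = 0.6) to 0.54 (f = 0.5, ρ = 0.4, d2 = 0.3).

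| L | Placebo-based for all (k = 0) | Some misrouted | All misrouted |
|---|---|---|---|
| 3 | 0.54–0.57 | 0.56–0.58 (k = 1) | 0.60 |
| 5 | 0.50–0.55 | 0.54–0.57 (k = 2) | 0.60 |

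The last column is 5–12% (L = 3) or 8–21% (L = 5) above the placebo-based value.

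A two-visit multiple-imputation simulation (ρ = 0.5, d2 = 0.30, 1,500 trials) agrees. With 2, 4 and 6 of 26 missing per arm, MAR against copy reference gave 0.596 against 0.562, 0.599 against 0.530, and 0.607 against 0.502. The formula predicts gaps of 0.45/26 = 0.0173 per subject, that is 0.035, 0.069 and 0.104.

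**6. Effect on the decision.** A paired simulation used 3,000 trials per scenario, 20 imputations, ANCOVA at Week 6 and Rubin's rules. At one-sided 0.10 the SAP rule rejected more often than copy reference, by 0.2 to 2.0 points (1 of 3 misrouted) up to 1.7 to 9.2 points (5 of 5). With no drug effect the mean estimates agreed within 0.002. Rejection was then 0.074–0.101 under the SAP rule and 0.059–0.086 under copy reference (Monte Carlo SE about 0.005).

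Copy reference with Rubin's variance is therefore conservative. In a further check (20,000 trials per scenario, unadjusted Week 6 difference, every leaver with a Week 2 score), each method was calibrated to 10% under the null. The gap became −3.6 to +0.9 points. In one 5-of-5 comparison, rejection was 0.745 against 0.674 raw and 0.762 against 0.764 calibrated.

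**The case against.** The MAR reading has support. The class is worded as events that lead to discontinuation, and a subject who leaves without giving a reason may have no identified event. Strategy 2 speaks of data recorded after the event, and a score never collected is not recorded data. The residual missing-data category appears in both documents. SAP 10.7.3.1 describes the tipping-point analysis as pressing on a MAR assumption in the main analysis. Protocol 13.6.2 makes placebo-distribution imputation for any missing active-arm data a sensitivity analysis, which would add less if most leavers were already handled that way.

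This keeps the MAR reading possible and limits confidence, but it remains the weaker one. Discontinuation has its own named class with COVID-19 as the sole exception, and the estimand's opening sentence names study discontinuation. Missed assessments in subjects still on treatment give the residual category content of its own.

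Two further points stand. Copy reference (SAP 10.7.3.2) runs unconditionally and is a key deliverable, so the placebo-based estimate will be reported beside the primary. The protocol also leaves imputation detail to the SAP, and Appendix B item 11 records that a definition was added, though not that it narrows the class.

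A reader might infer from the higher rejection rates that the rule inflates false positives. The null results do not support that, because the excess comes largely from conservative variance under copy reference. A reader might also take 12% or 21% as the expected overstatement. Those figures need every leaver to be misrouted and the least favourable assumptions, and the documents give no dropout data. The p < 0.05 trigger for the tipping-point analysis in Layout T17, set against a primary test at one-sided 0.10, is a separate issue and adds nothing here.

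**Conclusion.** Item 3 is wrong as written when set against the estimand on its better reading. It should be fixed; I hold this with moderate confidence because the MAR reading cannot be excluded. The harm is a primary point estimate that departs from its estimand. If the drug works, the excess is 0.009–0.023 SD per misrouted active leaver of 26, given a 0.60 SD on-treatment effect and the assumed correlation and Week 2 effect. The total depends on an undocumented number of leavers. With no drug effect and dropout unrelated to outcome, the two rules agree on average. Coded leavers with no later assessment are undetermined by the text, so two programmers could produce different primary results.

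**What to change.** - Define event 3 as permanent stop of study drug or study withdrawal before the Week 6 AISRS for any non-COVID reason. Identify it from the Termination Form and Study Drug Administration pages as well as the adverse-event page, and drop the later-assessments condition.
- Date it from the recorded discontinuation or the first permanently missed dose. Keep a pre-dose AISRS taken that day, which the same-day rule would otherwise blank.
- End the AISRS Week 6 analysis window on a fixed day instead of EOT, for example Day 44, which the theoretical-date rule already uses.
- Restrict step 1b to COVID-related missing values and values that do not follow a strategy 2 event. In step 2, impute both blanked and never-collected values from placebo.
- List the change in Appendix D.

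If MAR is intended for leavers without a coded adverse event, state it in the estimand and list it in Appendix D as a departure from the protocol.

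The cost is SAP wording, one window limit and flag programming. The CRF pages are already named in SAP 8.6, 8.7 and 11.1.1.4. If the drug works, the estimate will be slightly less favourable and power under Rubin's rules somewhat lower.
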